#### 6.1.7 *Multiple Signs or Symptoms*

If an AE consists of several signs or symptoms that can be represented by one single syndrome or diagnosis, the syndrome or diagnosis will be recorded in the eCRF as the AE instead of the individual signs or symptoms.

#### 6.1.8 *Worsening Signs*

Symptoms, syndromes or diagnoses present before the first administration of the IMP will be considered as AEs if they worsen after the start of the IMP.

## 6.2 Serious Adverse Events or Reactions

### 6.2.1 Definitions

A Serious Adverse Event (SAE) is any untoward medical occurrence or effect that at any dose:

- results in death;
- is life-threatening (at the time of the event);
- requires in patient hospitalization or prolongation of existing hospitalization;
- results in persistent or significant disability/incapacity;
- is a congenital anomaly/birth defect;
- or is an important medical event.

**Death:** the death of a patient enrolled in a clinical study is per se not an event, but an outcome. An AE resulting in a fatal outcome must be fully documented and reported, including if the death occurred after treatment end, and regardless of the causality relationship of the death to the IMP. The cause of the death is usually the AE. If the cause cannot be determined, the case will be considered an unexplained death.

**Life-threatening:** an AE that places the patient, in the view of the initial reporter (Investigator), at immediate risk of death from the AE as it occurred, i.e. it does not include an AE that, had it occurred in a more severe form, might have caused death.

**Hospitalization:** an AE requiring an unplanned inpatient hospital admission, including at least an overnight stay. Of note: when standard practice for liver biopsy requires overnight hospitalization, this shall not be considered as an adverse event.

**Disability:** a substantial disruption of a person's ability to conduct normal life functions.

**Important medical event:** an important medical event that may not result in death, be life-threatening, or require hospitalization may be considered as a SAE when, based upon appropriate medical judgement, it may jeopardize the patient and may require medical or surgical intervention to prevent one of the outcomes listed in the definition. The concept includes AEs which suggest a significant hazard, contraindication or precaution for use, occurrence of malignancy or development of drug dependency or drug abuse.

**Overdose:** an overdose of an IMP is the accidental or intentional administration of a dose higher than the highest dose under clinical investigation. An overdose will be documented and reported to the safety officer (SO) in the same way as a SAE even if no toxic effects were observed.

**Pregnancy:** The occurrence of a pregnancy of a study patient or a partner of a study patient discovered during IMP administration or within 1 week after last administration of the IMP, is to be communicated to the Sponsor in an expedited manner with the same procedure and timelines as for SAEs (see section 6.2.2), independently from the occurrence of an AE. Specific follow-up of the event will be requested by the Sponsor until pregnancy outcome, at least on a quarterly basis as described in paragraph 10.1.

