The laboratory assessments performed at screening and end-of-treatment will include: haematology (CBC), blood biochemistry (ALT, AST,  $\gamma$ GT, alkaline phosphatase, total bilirubin, conjugated bilirubin, ultra-sensitive CRP, total cholesterol, triglycerides, HDL cholesterol, LDL cholesterol, creatinine, fasting glucose, insulin, HgbA1c, albumin, CPK, sodium, potassium, calcium), and two serum bank samples.

Urine Samples will be collected at V0 (*including urine pregnancy test*), V2, V3 and V4. Urine analysis by dipstick evaluating hematuria will be done on site. Urine samples will then be stored for further assessment and/or for safety evaluation.

Trough plasma levels of lanifibranor will be assessed at V1 and V3.

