**Figure 2: Lanifibranor Reduces Inflammation and Steatosis in a 3 Weeks MCD Model**

### IVA337 effect on inflammation

### IVA337 effect on steatosis

#### 1.4.2 Pharmacokinetics

Lanifibranor is considered as a class II compound as regard to the Biopharmaceutics Classification System (BCS) Guidance: high permeability and low solubility. It was evidenced in all tested species that lanifibranor absorption is dependent on the drug substance form and formulation, leading to a bioavailability in animals from 15% up to >80%. An enterohepatic recycling was evidenced, and a food effect was observed in human in the presence of high fat breakfast.

After oral administration in human, maximum plasma levels ( $C_{max}$ ) of lanifibranor were reached at about 1.0-3.5 h, and terminal plasma elimination half-life was around 10-15 h. Both Area Under the Curve (AUC) and  $C_{max}$  increased in a linear but slightly less than dose-proportional manner. Steady-state lanifibranor concentrations were generally achieved by Day 3 after daily dose administration, with no significant accumulation.

The mean apparent volume of distribution  $V_z/F$  ranged from 318 to 607 L in healthy subjects. Lanifibranor was extensively distributed in monkeys (~10 L/kg). IVA337 binds very highly to plasma proteins in all tested species (~99.9%) and no affinity to blood cells was observed. By autoradiography in rat, lanifibranor was shown to be mainly distributed in the excretory organs (liver, kidneys, lungs, gastrointestinal tract) and in placenta in pregnant rats with no affinity for the melanin tissues and with very limited central nervous system penetration.

Lanifibranor-related radioactivity elimination was mainly faecal (>85%) and the urinary excretion was minor (<7%) with a very low renal clearance. The excretion was essentially complete after 3 days.

AUC indicated approximately 23% of the radioactivity in plasma were related to lanifibranor, while 77% were related to its metabolites. Lanifibranor was observed *in vitro* to be metabolized either by enzymes of phase I (mainly via CYP isoforms CYP2C8, 2C19 and 3A4) and phase II (mainly via UGT 2B7, 1A1 and 1A3). No affinity of lanifibranor to uptake or efflux transporters as substrate was evidenced *in vitro*.

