**Table 3: Interspecies Comparison of Human and Animal Plasma Exposure to Lanifibranor in General Toxicity Studies**

Human Plasma AUC at Estimated Active Dose (µg.h/mL)	Species	NOAEL		AUC at NOAEL	Safety Margin
		Male-Female		Male-Female	
		(mg/kg/d)		(µg.h/mL)	
50	Mouse*	25		225 - 278	~5
	Rat**	2000 1000	-	798 - 1144	16 - 23
	Monkey###	1000		110 - 82	1.6 - 2.2

\*: from 13-week toxicology study in CD-1 mice

\*\* : from 13-week toxicology study in Wistar rats

###: from 26-week toxicology study in Cynomolgus monkeys

**Table 4 : Interspecies Comparison of Human and Animal Plasma Exposure to Lanifibranor in Segment II Reproductive Toxicity Studies**

Species/Strain	NOAEL (mg/kg/d)	Plasma Exposure (AUC0-24 as µg.h/mL)	
		Gender	lanifibranor
Han Wistar Rat	100	Female	437 (8.7) 
New Zealand White Rabbit	3	Female	105 (2.1)

 values in brackets show exposure margin factor to clinical exposure

The safety margins over expected human exposure in general toxicology studies were at least 20-fold in rats and 2-fold in monkeys (

Table 3). The safety margins over expected human exposure established in segment II reproductive toxicity studies were 9-fold in rats and 2-fold in rabbits (Table 4). A preliminary 2-week pharmacokinetic and toxicity study in the mouse, where plasma exposures were markedly higher than those achieved in volunteers given the highest tested dose of 1500 mg/day for two weeks (approximately 40-fold) and higher than those achieved in the chronic rat study, has evidenced signs of toxicity for the kidney, the heart and the skeletal muscles, in particular myositis of skeletal muscles, minimal to moderate myocarditis and tubulo-interstitial nephritis. These organs are known targets for toxicity of PPAR agonists. However, a recently conducted 13-week study in mice established an adequate 5-fold safety margin over expected human exposure at a NOAEL (no observed adverse effects levels) of 25 mg/kg/day.

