  8. Negative pregnancy test or post-menopausal. Women with childbearing potential (i.e. fertile, following menarche and until becoming post-menopausal unless permanently sterile) must be using a highly effective method of contraception (i.e. combined (estrogen and progestogen containing) hormonal/ progestogen-only hormonal contraception associated with inhibition of ovulation, intrauterine device, intrauterine hormone-releasing system, bilateral tubal occlusion, vasectomised partner). The contraceptive method will have to be followed for at least one menstruation cycle after the end of the study
  9. Subjects having given her/his written informed consent.

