## **10. Patient Withdrawal & Replacement**

### **10.1 Patient Withdrawal**

Participation in the study is strictly voluntary. The patients have the right to withdraw from the study at any time for any reason, without the need to justify. The Investigator also has the right to withdraw patients in case of safety concerns, protocol deviations or administrative reasons. Since an excessive rate of withdrawals can render the study uninterpretable, the unnecessary withdrawal of patients must be avoided.

Reasons of withdrawal include, but are not limited, to the following:

- Patient decision
- Lost to follow-up, death

- Any AE, laboratory abnormality or illness which, in the opinion of the Investigator, indicates that continued treatment with study therapy and participation in the trial is not in the best interest of the subject.
- Major protocol deviation: e.g. lack of compliance with scheduled visits, non-compliance with study treatment, treatment with prohibited medication during the study (see 22)
- Any deterioration in cardiac status
- ALT or AST > 8 x ULN; or if ALT or AST > 5xULN for more than 2 weeks; or if ALT or AST > 3xULN and bili (total) > 2xULN (or INR>1.5); or ALT or AST > 3xULN and symptoms (Right Upper Quadrant pain, nausea, ...)
- Investigator's decision for any other reason

If a patient discontinues the study, the Investigator will make reasonable efforts to obtain the reason and to perform all protocol-defined end of study assessments as soon as possible. The reason and circumstances for premature discontinuation (e.g. consent withdrawal, AE, lost to follow up, etc.), and the date of withdrawal must be documented in the eCRF. If a patient discontinues the study for safety reasons, the outcome must be known.

In the case of withdrawal due to pregnancy (see paragraph 6.2.1), the patient will be followed until outcome, i.e. at least on a quarterly basis for follow-up evaluation of the pregnancy, foetus, delivery and new born. In the case of withdrawal due to an AE the patient will be followed until resolution of the AE, or until in the opinion of the Investigator the event has stabilized, and the patient is referred to their primary physician for appropriate management of the ongoing event. Reasonable efforts will be made to contact a patient who fails to attend any follow-up appointments, in order to ensure that he/she is in satisfactory health.

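### Pregnancy reporting depends on discovery by 1 week after the last dose, so a pregnancy conceived under exposure late in dosing can fall outside the rule even if disclosed at V4

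*Protocol*

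**What the plan says.** Protocol section 6.2.1 sets the reporting duty. It covers "The occurrence of a pregnancy of a study patient or a partner of a study patient" that is "discovered during IMP administration or within 1 week after last administration of the IMP". Such a case goes to the sponsor on the SAE timeline, whether or not an adverse event has occurred. For that event, "Specific follow-up of the event will be requested by the Sponsor until pregnancy outcome", at least quarterly.

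Section 10.1 has a second follow-up clause: "In the case of withdrawal due to pregnancy (see paragraph 6.2.1), the patient will be followed until outcome". It applies to withdrawals caused by pregnancy.

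Inclusion criterion 8 (section 4.2.1 and synopsis) applies to women of childbearing potential: "The contraceptive method will have to be followed for at least one menstruation cycle after the end of the study". Section 5.3.6 makes V4, at week 28, the end-of-study visit.

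On testing, section 4.1.1 provides a serum test at screening, which Table 2 repeats if screening exceeds 4 weeks. The synopsis then says: "Urine Samples will be collected at V0 (*including urine pregnancy test*), V2, V3 and V4". Section 5.2.2 says the same. Neither the text nor Table 1 places a pregnancy test at V1 to V4.

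**The concern.** A rule based on discovery works only if discovery is prompt. Here nothing scheduled after V0 would reveal a pregnancy, so in practice it depends on the patient noticing. A woman who conceives in the last week of dosing would not ordinarily know within 7 days of her last tablet. If she tells the investigator at V4, section 6.2.1 does not oblige anyone to report the pregnancy or follow it, although the conceptus was exposed. Section 10.1 does not help, because a patient who completed treatment has not withdrawn. The same gap follows early discontinuation for another reason, since the clock starts at the last dose.

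At stake is outcome information on exposed pregnancies for a drug whose margins over expected human exposure, established in "segment II reproductive toxicity studies were 9-fold in rats and 2-fold in rabbits" (section 1.4.3), are limited in the rabbit, and which was found "in placenta in pregnant rats" (section 1.4.2).

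**Working it through.** The plan states no figure to reproduce. The check is a comparison of dates, followed by a simple range.

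**Inputs from the documents**
- Treatment: 24 weeks = 168 days (section 4.3.3).
- Pregnancy reporting closes at last dose + 7 days = day 175, week 25 (section 6.2.1).
- V4: week 28 = day 196 (section 5.3.6).
- Post-treatment safety phase: 30 days (section 4.1.3). SAP treatment-emergent window: 28 days after the last dose (SAP 4.5.6.2).
- Contraception: to at least one cycle after the end of the study (criterion 8).
- Half-life about 10 to 15 h, with excretion essentially complete after 3 days (section 1.4.2).

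**Assumptions, not in the documents**
- Recognition lag L of 14, 28 or 42 days after conception.
- Conceptions spread evenly over the 168 days.
- A cycle of 28 days (range 21 to 35).

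**Step 1: the calendar.** Pregnancy reporting closes 28 − 25 = 3 weeks before V4, while the patient is still in the study and adverse events are still being collected. Contraception runs to about week 28 + 4 = 32 (31 to 33), which is 7 weeks (6 to 8) past the reporting window.

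**Step 2: which on-treatment conceptions are missed.** A conception on day c is recognised on day c + L. It is outside the rule if c + L > 175, that is, c > 175 − L. The affected part of the course is 168 − (175 − L) = L − 7 days.

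| L (days) | Affected end of course | Share of on-treatment conceptions |
|---|---|---|
| 14 | 7 days | 7/168 = 4.2% |
| 28 | 21 days | 21/168 = 12.5% |
| 42 | 35 days | 35/168 = 20.8% |

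**Step 3: how many of these would surface by V4.** Recognition by day 196 needs c ≤ 196 − L. For L = 14 or 28, every affected conception is recognised by V4. For L = 42, those up to day 154 are recognised by then, which is 154 − 133 = 21 of the 35 affected days. The other 14 days surface after V4, when no contact is scheduled.

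**Step 4: exposure after the last dose.** One week is 7 × 24 = 168 h, or 168/15 = 11.2 to 168/10 = 16.8 half-lives. Conceptions well after the last dose therefore mostly follow elimination, and they are left out of the shares above.

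**The case against.** Several points on the other side are sound.

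- **One week is not arbitrary.** With the half-life and excretion figures in section 1.4.2, 7 days is ample as an exposure window. This stands. It shows that the weakness is the choice of discovery as the trigger, not the length of the period. A reader might infer that every conception between the reporting cut-off and the end of the contraception period is a missed exposed pregnancy. The documents do not support that: they never call the contraception period a risk period, and most of it lies after elimination.
- **Other routes exist.** Section 3.5 asks investigators to inform the sponsor of information that might affect the benefit-risk evaluation. Section 6.2.1 makes a congenital anomaly an SAE. Section 6.2.2 keeps SAEs reportable after the last visit if the investigator suspects the product or a protocol procedure. Unscheduled visits (section 5.3.7) could also bring a pregnancy to light, and nothing forbids a voluntary report. So it would be too strong to say that late conceptions escape reporting altogether. These routes are still general or conditional on an adverse outcome, and none requires an uncomplicated pregnancy to be followed to outcome.
- **The toxicology is not alarming.** Section 1.4.3 states that no potential risks were identified from studies that include the reproductive ones, and the 2-fold and 9-fold margins are at no-effect levels. This stands. The concern is loss of information, not a demonstrated hazard.
- **Numbers will be small.** Highly effective contraception is an entry condition. The percentages are shares of an unstated and probably very low count.
- **Partners.** Criterion 8 sets no contraception period for the partners of male patients, whereas section 6.2.1 covers partner pregnancies. Copying the contraception period into the reporting rule would therefore leave the partner window undefined.

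**Conclusion.** The gap is real but narrow. Followed as written, section 6.2.1 does not require a report or follow-up for a pregnancy conceived under exposure late in dosing and recognised more than 7 days after the last dose, even if it is disclosed at V4. If recognition takes 2 to 6 weeks, this affects conceptions in roughly the last 1 to 5 weeks of treatment, or 4% to 21% of on-treatment conceptions if these are evenly spread. Both the lag and the even spread are assumptions, and the absolute number is expected to be small. The mismatch in the text and the 3-week gap before V4 need no assumption about recognition.

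The finding does not touch the primary endpoint, the analysis sets or error control. It warrants a correction to the safety-reporting text.

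**What to change.** Amend the pregnancy paragraph of section 6.2.1 in three respects:

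1. Key the duty to estimated date of conception or exposure instead of date of discovery.
2. State that pregnancies in patients or partners disclosed at any time up to and including V4 are reported and followed to outcome under the existing quarterly arrangement.
3. Reconcile the paragraph with criterion 8 in section 4.2.1 and the withdrawal clause in section 10.1, and say how the window applies to partners. No change to the contraception rule itself is proposed here.

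The matching line in the safety-reporting instructions should change with it. The cost is a short wording amendment and a few extra pregnancy reports to follow. One limit remains: with slow recognition (6 weeks in the working), conceptions in the last 2 weeks of dosing surface after V4. No contact is scheduled then, so the sponsor should state how such late disclosures would be handled.

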### 6.2.2 Immediate reporting

The Investigator will immediately, i.e. within 24 hours from first knowledge, report any SAE occurring during the study to the safety officer (SO) acting on behalf of the Sponsor of the study:

STRAGEN SERVICES S.A.S, [name]  
[contact], [contact],  
Email:

The Investigator will complete in English and sign a SAE Report Form and transmit it to the SO by email or telefax not later than 24 hours after the first knowledge of the SAE. The SO acknowledges the receipt of the SAE information by email to the investigational site within one working day. In the absence of email acknowledging the receipt or in case of issue in sending the fax or email, the Investigator shall contact the SO by any means for ensuring the receipt of SAE information at the earliest opportunity.

Any follow-up information will be reported to the SO and to the Sponsor as soon as it becomes known, with the same process and timelines as described here above for initial reports. As per Article 17 of the European Directive 2001/20/EC, the Sponsor will ensure that all relevant information about SAE and suspected serious unexpected adverse reactions (SUSAR) is recorded and reported to the national CA in all Member States concerned and to Ethics Committee within the applicable timeframe.

Serious adverse events occurring after the last study visit will only be reported if the Investigator believes that the event may have been caused by the IMP or a protocol procedure.

Hospitalization for a diagnosis or therapeutic procedure planned before study enrolment but performed after the enrolment should not be considered for SAE and should be reported in eCRF in concomitant procedures page.

### **6.3 Safety Variables**

All safety variables will be primary ones. Safety evaluations will be completed as given in section 9.7 and as indicated below.

The Investigator will rate all safety variables as to clinical relevance or not. In case of a clinically relevant abnormality, the safety evaluation will be repeated. If the abnormality is confirmed and clinically relevant, it will be recorded as an AE term in the eCRF. The abnormality will be followed up until the value has returned to normal or an adequate explanation is found.

#### *6.3.1 Physical Examination*

Physical examinations will be conducted by the Investigator. Any findings will be documented in the source document and recorded in the eCRF.

#### *6.3.2 Laboratory Tests*

Laboratory tests will be analyzed by a central laboratory (CL). In the aim of maintaining the “double-blind”, some biological values will be blinded on Central laboratory reports/records until the end of the study and could be unblinded only on DSMB members request. In this case, an independent data-management team will be indentify at KEYRUS BIOPHARMA to perform the data-transfert of theses biological value.

Additional samples for laboratory safety variables may be drawn at any time during the study at the Investigators judgement. The laboratory assessments performed at each visit are listed in the following table (see Table 7 and Table 8).

**Table 7 : Central laboratory tests for safety assessment**

Domain	Goal	Test	Screen	V0	V1	V2	V3	V4
Bone	Safety	B-Crosslaps	-	✓	-	-	✓	-
	Safety	Osteocalcin	-	✓	-	-	✓	-
Chemistry	Safety	Creatinine	✓	✓	✓	✓	✓	✓
	Safety	CPK	✓	✓	✓	✓	✓	✓
	Safety	Urea	✓	✓	✓	✓	✓	✓
	Safety	Albumin	✓	✓	✓	✓	✓	✓
Hematology	Safety	Hb	✓	✓	✓	✓	✓	✓
	Safety	RBC	✓	✓	✓	✓	✓	✓
	Safety	Platelets	✓	✓	✓	✓	✓	✓
	Safety	WBC (Diff Count)	✓	✓	✓	✓	✓	✓
	Safety	MCV	✓	✓	✓	✓	✓	✓
	Safety	CCMH	✓	✓	✓	✓	✓	✓
	Safety	Hematocrit	✓	✓	✓	✓	✓	✓
	Safety	Reticulocytes	✓	✓	✓	✓	✓	✓
Inflammation	Safety	Nt-ProBNP	-	✓	-	-	✓	-
liver	Safety	INR	✓	✓	✓	✓	✓	✓

**Table 8 : Central Laboratory tests for efficacy assessment**

Domain	Goal	Test	Screen	V0	V1	V2	V3	V4
	Efficacy	TIMP-1	-	✓	-	-	✓	-
	Efficacy	TIMP-2	-	✓	-	-	✓	-
	Efficacy	cytokeratin K18	-	✓	-	-	✓	-
	Efficacy	hyaluronic acid	-	✓	-	-	✓	-
	Efficacy	P3NP	-	✓	-	-	✓	-
Fibrosis	Efficacy	FGF 21	-	✓	-	-	✓	-
	Efficacy	Insulin	-	✓	-	-	✓	-
	Efficacy	Fasting glucose	✓	✓	✓	✓	✓	✓
	Efficacy	HbA1c	✓	✓	✓	✓	✓	✓
	Efficacy	peptide C	-	✓	-	-	✓	-
	Glucids	Efficacy	fructosamine	-	✓	-	-	✓
	Efficacy	Plasma Iron	✓	-	-	-	✓	-
	Efficacy	Transferrin	✓	-	-	-	✓	-
	Chemistry	Efficacy	Ferritin	✓	-	-	✓	-
	Efficacy	Fibrinogen	-	✓	-	-	✓	-
	Efficacy	hs-CRP	-	✓	-	-	✓	-
	Efficacy	Alpha2-macrogulin	-	✓	-	-	✓	-
	Inflammation	Efficacy	Haptoglobin	-	✓	-	-	✓
	Efficacy	Triglycerides	✓	✓	✓	✓	✓	✓
	Efficacy	HDL-C	✓	✓	✓	✓	✓	✓
	Efficacy	LDL-C	✓	✓	✓	✓	✓	✓
	Efficacy	Total-C	✓	✓	✓	✓	✓	✓
	Efficacy	FFA	-	✓	-	-	✓	-
	Efficacy	APO A1	-	✓	-	-	✓	-
	Efficacy	Adiponectin	-	✓	-	-	✓	-
Lipids	Efficacy	Leptin	-	✓	-	-	✓	-
	Efficacy	ALT	✓	✓	✓	✓	✓	✓
	Efficacy	AST	✓	✓	✓	✓	✓	✓
	Efficacy	AlcPhos	✓	✓	✓	✓	✓	✓
	Efficacy	Bilirubin total	✓	✓	✓	✓	✓	✓
	Liver	Efficacy	GGT	✓	✓	✓	✓	✓

